4.3. Protocol Deviations

A summary of important protocol deviations will be provided by the Clinical Operations group for subjects in the Safety Analysis Set.

Subjects who received study drug other than their enrolled treatment assignment will be listed with the start and stop dates that they received incorrect study treatment.

5. BASELINE CHARACTERISTICS

5.1. Demographics

Subject demographic variables (ie, age, sex, race, and ethnicity) will be summarized by HCV genotype (1 [further broken down to 1a and 1b], 2, 3, 4, 5, 6, or other, as appropriate, and total) using descriptive statistics (n, mean, SD, median, Q1, Q3, minimum, and maximum) for age, and using the numbers and percentages of subjects for sex, race, and ethnicity. Age is calculated in years at the date of initial study drug administration. If a subject did not receive study drug after enrollment, the subject's age will be calculated from the date that the subject signed the informed consent form. The summary of demographic data will be provided for the Safety Analysis Set.

A by-subject demographic listing will be provided by subject ID number in ascending order.

5.2. Other Baseline Characteristics

Other baseline characteristics include:

- weight in kg
- height in cm
- body mass index (BMI; in kg/m²)
- HCV genotype (1 [further broken down to 1a and 1b], 2, 3, 4, 5, 6, or other, as appropriate, and as determined by sequencing if available)
- cirrhosis (presence, absence, not determined)
- primary assessment method used to make the cirrhosis determination (liver biopsy, transient elastography, Fibrotest and APRI, APRI, Fibrotest, liver imaging, other)
- transient elastography in kPa
- Fibrotest as a continuous and as categorical variable
- APRI
- FIB-4 (ie, $\frac{\text{Age (years)} \times \text{AST (U/L)}}{\text{Platelet Count (10}^3\text{/uL)} \times \sqrt{\text{ALT (U/L)}}}$)
- IL28B (CC, CT, TT)
- baseline HCV RNA (IU/mL) (< 800,000 IU/mL, ≥ 800,000 IU/mL)

- baseline HCV RNA (\log_{10} IU/mL) as a continuous variable and as categories ($< 6 \log_{10}$ IU/mL, $\geq 6 \log_{10}$ IU/mL)
- baseline ALT (U/L) as a continuous variable and as categories ($\leq 1.5 \times \text{ULN}$, $> 1.5 \times \text{ULN}$)
- estimated glomerular filtration rate (eGFR) using Schwartz Formula ($\text{mL}/\text{min}/1.73\text{m}^2$)
- prior treatment experience (treatment naïve, treatment experienced [DAA-naïve, DAA-experienced])
- number of prior HCV treatments
- most recent response to prior HCV treatment (non-response, relapse/breakthrough) for treatment experienced subjects
- mode of HCV Infection
- bone age in years
- Tanner Stage

Estimated glomerular filtration rate will be calculated using Schwartz Formula ($\text{mL}/\text{min}/1.73\text{m}^2$) $k \times L/\text{Scr}$ [(k is a proportionality constant, for adolescent females ≥ 12 years old is 0.55; for adolescent males ≥ 12 years old is 0.70); L is height in centimeters (cm); and Scr is serum creatinine (mg/dL)]

These baseline characteristics will be summarized by HCV genotype (1 [further broken down to 1a and 1b], 2, 3, 4, 5, 6, or other, as appropriate, and as determined by sequencing, and total) using descriptive statistics (n, mean, SD, median, Q1, Q3, minimum, and maximum) for continuous variables and using the numbers and percentages of subjects for categorical variables. The summary of baseline characteristics will be provided for the Safety Analysis Set.

A by-subject listing of other baseline characteristics will be provided by subject ID number in ascending order.

5.3. Swallowability Assessment for SOF/VEL/VOX FDC Placebo Tablets

For subjects in the 12 to <18 years of age group, swallowability of SOF/VEL/VOX FDC placebo tablets will be summarized using the numbers and percentages of subjects in each swallowability category (ie, Able to Swallow, Unable to Swallow).

A by-subject listing of Swallowability of SOF/VEL/VOX FDC placebo tablets will be provided by subject ID number in ascending order.

5.4. Acceptability and Palatability of SOF/VEL/VOX FDC

A questionnaire will be administered to subjects to assess acceptability and palatability of the formulation they received on Day 1, End of Treatment and Early Termination (as applicable). If the subject is unable to complete the questionnaires, the parent/legal guardian will assist to complete the questionnaire on their behalf. The subject's parent/legal guardian will also complete a questionnaire on End of Treatment or Early Termination (as applicable) for their assessment of acceptability of the formulation the subject received.

Acceptability and palatability will be assessed by character response to questions about how the study drug tasted, how easy it was to swallow the study drug, and also at the end of treatment about how it was to take the study drug and, for those who received that tablet formulation, how they felt about the number of tablets they had to swallow in the following categories, as applicable:

- Did Not Taste the Study Drug (for question regarding study drug taste only)
- Very Bad/Hard
- Bad/Hard
- Maybe Bad/Hard or Maybe Good/Easy
- Good/Easy
- Very Good/Easy

Responses to the acceptability and palatability questionnaire by subjects and their parent/legal guardian at Day 1, End of Treatment and Early Termination (as applicable) will be respectively summarized using the numbers and percentages of subjects in the corresponding categories, as applicable, for each question.

A by-subject listing of acceptability and palatability of SOF/VEL/VOX FDC will be provided by subject ID number in ascending order.

5.5. Medical History

General medical history (ie, conditions not specific to the disease being studied) data will be collected at screening and listed only. General medical history data will not be coded. A by-subject listing of disease-specific medical history will be provided by subject ID number (in ascending order) and medical history of abnormalities (in chronological order).

6. EFFICACY ANALYSES

6.1. Key Efficacy Endpoint

6.1.1. Definition of the Key Efficacy Endpoint

The key efficacy endpoint is SVR12 defined as HCV RNA < LLOQ (ie, < 15 IU/mL) 12 weeks after discontinuation of the study drug in the FAS. The COBAS® AmpliPrep/COBAS® TaqMan® HCV Test, v2.0 for use with the High Pure System will be used to measure HCV RNA.

6.1.2. Analysis Methods for the Key Efficacy Endpoint

No inferential statistics will be provided for efficacy endpoints. No statistical comparison will be conducted.

The point estimates of SVR12 rate and 2-sided 95% exact CI based on Clopper-Pearson method {Clopper 1934} will be provided by HCV genotype (1 [further broken down to 1a and 1b], 2, 3, 4, 5, 6, or other, as appropriate, and total).

6.1.3. Subgroup Analysis of the Key Efficacy Endpoint

The point estimates of SVR12 rate and 2-sided 95% exact CIs based on Clopper-Pearson method {Clopper 1934} will be provided within each subgroup specified in Section 3.4

A Forest plot will graphically present estimates and 95% confidence intervals of SVR12 rates within each subgroup.

6.2. Secondary Efficacy Endpoints

6.2.1. Definition of Secondary Efficacy Endpoints

- The percentage of subjects who attain SVR at 4 and 24 weeks after stopping therapy, defined as HCV RNA < LLOQ (ie, < 15 IU/mL) 4 and 24 weeks after stopping treatment (SVR 4 and SVR 24)
- The percentage of subjects with HCV RNA below LLOQ by study visit
- HCV RNA (\log_{10} IU/mL) and change from baseline in HCV RNA (\log_{10} IU/mL) through end of treatment (EOT)

- The percentage of subjects with virologic failure as the following:

On-treatment virologic failure

HCV RNA \geq LLOQ after having previously had HCV RNA $<$ LLOQ, while on treatment, confirmed with 2 consecutive values (note, second confirmation value can be posttreatment), or last available on-treatment measurement with no subsequent follow-up values (ie, breakthrough)

$> 1 \log_{10}$ IU/mL increase in HCV RNA from nadir while on treatment, confirmed with 2 consecutive values (note, second confirmation value can be posttreatment), or last available on-treatment measurement with no subsequent follow-up values (ie, rebound)

HCV RNA persistently \geq LLOQ through 8 weeks of treatment (ie, nonresponse)

Relapse

HCV RNA \geq LLOQ during the posttreatment period having achieved HCV RNA $<$ LLOQ at end of treatment, confirmed with 2 consecutive values or last available posttreatment measurement

- The proportion of subjects with ALT normalization (defined as ALT $>$ ULN at baseline and ALT \leq ULN at each visit), presented by study visit
- Characterization of HCV drug resistance substitutions at baseline, during, and after therapy with SOF/VEL/VOX

6.2.2. Analysis Methods for Secondary Efficacy Endpoints

For analyses of HCV RNA $<$ LLOQ by visit while on treatment and during the posttreatment (SVR) follow-up period, subjects will be assigned a value at each visit based on the analysis visit windows specified in Section 3.7.2. Missing values will be imputed based on the categorical imputation rules described in Section 3.5.1. The 2-sided 95% exact confidence interval based on Clopper-Pearson method will be provided for the percentage of subjects with HCV RNA $<$ LLOQ at each visit. The overall category for “HCV RNA $<$ LLOQ” will be split into the following 2 subcategories: “ $<$ LLOQ TND” for subjects with target not detected and “ $<$ LLOQ detected” for subjects with $<$ LLOQ detected in tabular displays.

Graphs for the percentage of subjects with HCV RNA $<$ LLOQ over time during treatment will be displayed.

Summary statistics will be presented for absolute values and change from baseline in HCV RNA (\log_{10} IU/mL) by visit through EOT. Imputation rules described in Section 3.5.1 will be used to assign HCV RNA values for missing values at a visit that are bracketed by “ $<$ LLOQ TND” and/or “ $<$ LLOQ detected”. Otherwise, a missing excluded analysis will be performed. Plots of the mean \pm SD and median (Q1, Q3) of absolute values and changes from baseline in HCV RNA through EOT will be presented.

For the SVR12 endpoint analysis, a summary table of the number and percentage of subjects with SVR12, virologic failure (VF), and Other will be created by HCV genotype (1 [further broken down to 1a and 1b], 2, 3, 4, 5, 6, or other, as appropriate, and total). All subjects who achieve SVR12 will be categorized as SVR12. Virologic failure will be descriptively summarized as “on-treatment virologic failure” and relapse (which will be broken down by study drug completed yes/no). Subjects who do not achieve SVR12 and do not meet criteria for VF will be categorized as Other. The denominator for relapse will be the number of subjects who had HCV RNA < LLOQ on their last observed on-treatment HCV RNA measurement; otherwise, the denominator will be the number of subjects in the FAS.

A concordance table between SVR12 and SVR24 will be provided. Subjects with both observed SVR12 and observed SVR24 data will be included for this analysis.

In addition, a summary table of the number and percentage of subjects with HCV RNA < LLOQ and \geq LLOQ at the posttreatment follow-up visit (observed and imputed, with reasons for imputed) will be provided for each posttreatment follow-up visit. 95% Clopper-Pearson exact CIs will be presented for the overall proportion of subjects with HCV RNA < LLOQ.

Tables for ALT normalization by visit will use similar methodology to the analyses of HCV RNA < LLOQ, but will use a missing excluded analysis. Only those subjects with ALT greater than the ULN range at baseline (defined as the last ALT value collected prior to first dose of study drug) will be included in the analysis of ALT normalization.

Drug resistant substitutions will be analyzed as part of the Virology Study Report.

CCI

[REDACTED]

[REDACTED]

[REDACTED]

[REDACTED]

[REDACTED]

[REDACTED]

CCI

[REDACTED]

[REDACTED]

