3. GENERAL CONSIDERATIONS FOR DATA ANALYSES

Analysis results will be presented using descriptive statistics. For categorical variables, the number and percentage of subjects in each category will be presented; for continuous variables, the number of subjects [n], mean, standard deviation [SD] or standard error [SE], median, first quartile [Q1], third quartile [Q3], minimum, and maximum will be presented.

Data collected in the study will be presented in by-subject listings for all subjects in the Safety Analysis Set, unless otherwise specified. All by-subject listings will be presented by subject identification (ID) number in ascending order, unless otherwise specified.

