3.2. Subject Grouping

For analyses based on the All Enrolled Analysis Set or FAS, subjects will be grouped according to the treatment to which they were enrolled. For analyses based on the Safety Analysis Set, subjects will be grouped according to the actual treatment received. The actual treatment received is defined as the enrolled treatment except for subjects who received treatment that differs from the enrolled treatment for the entire treatment duration. In this case, the actual treatment received is defined as the treatment received for the entire treatment duration. Given the fact that only DAA-naïve subjects without cirrhosis have been enrolled in this study, there will be only one treatment group (ie, SOF/VEL/VOX FDC 8 weeks).

The efficacy analyses will be performed on the FAS, and for selected efficacy analyses, by HCV genotype (1 [further broken down to 1a and 1b], 2, 3, 4, 5, 6, or other, as appropriate, and total). The safety analysis will be performed on the Safety Analysis Set.

For other selected analyses, for example, the summary of responses to the acceptability and palatability questionnaire, the analysis of tanner pubertal stage assessment data, please refer to the relevant sections for the detailed description of subject grouping.

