3.5. Missing Data and Outliers

3.5.1. Missing Data

In general, missing data will not be imputed unless methods for handling missing data are specified.

For missing last dosing date of study drug, imputation rules are described in Section 3.7.1. The handling of missing or incomplete dates for adverse event (AE) onset is described in Section 7.1.5.2, and for prior and concomitant medications in Section 7.8.

For analyses of categorical HCV RNA data, missing posttreatment HCV RNA data will have the missing data imputed. Missing on-treatment HCV RNA will have the missing data imputed up to the time of the last dose (for on-treatment displays). If the study day associated with the last dosing date is greater than or equal to the lower bound of a visit window, and the value at the visit is missing, the value will be imputed. If the study day associated with the last dosing date is less than the lower bound of a visit window, then the on-treatment value at that visit will remain missing.

If a data point is missing and is preceded and followed in time by values that are “< lower limit of quantitation (LLOQ) target not detected (TND)”, then the missing data point will be set to “< LLOQ TND”. If a data point is missing and preceded and followed by values that are “< LLOQ detected”, or preceded by “< LLOQ detected” and followed by “< LLOQ TND”, or preceded by “< LLOQ TND” and followed by “< LLOQ detected”, then the missing value will be set to “< LLOQ detected”. In these situations, the data point will be termed a bracketed success; otherwise, the data point will be termed a bracketed failure (ie, \geq LLOQ detected). If a data point is missing and is not bracketed, the missing data point will also be termed a failure (ie, \geq LLOQ detected) except for SVR24, which will be imputed according to SVR12 status. Success for SVR12 who have no further HCV RNA measurements collected will be counted as a success for SVR24 due to the high correlation between these 2 endpoints.

For the analyses of continuous HCV RNA efficacy data, when and only when a missing HCV RNA value is imputed as < LLOQ TND or < LLOQ detected according to the imputation rule described above, the corresponding continuous value will be imputed to LLOQ - 1 IU/mL. No other imputation will be performed for continuous HCV RNA data.

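### Could a subject who relapses, is retreated outside the study and then tests negative be counted as SVR12?

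*SAP*

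**What the plan says.** SAP 6.1.1: "The key efficacy endpoint is SVR12 defined as HCV RNA < LLOQ" (15 IU/mL) 12 weeks after study drug is stopped. SVR4 and SVR24 are defined the same way in SAP 6.2.1. Follow-up days are counted from the last dose of study drug (Protocol 8.2; SAP 3.7.2). The HCV RNA windows in SAP Table 3-2 are days 21 to 69 (FU-4), 70 to 146 (FU-12) and 147 to 210 (FU-24). The latest record in each window is used (SAP 3.7.3).

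SAP 6.2.2 sorts subjects into SVR12, virologic failure and Other, and gives SVR12 precedence: "All subjects who achieve SVR12 will be categorized as SVR12". Relapse (SAP 6.2.1) is a posttreatment value at or above LLOQ "confirmed with 2 consecutive values or last available posttreatment measurement".

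The imputation rules (Protocol 8.3; SAP 3.5.1) deal with missing values only. They include a carry-forward: "Success for SVR12 who have no further HCV RNA measurements collected will be counted as a success for SVR24". No readable passage mentions HCV RNA measured after non-study HCV therapy. The text between SAP 6.2.2 and 6.4, Protocol 6.5 and a block after Protocol 3.7 are redacted.

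**The concern.** SVR is meant to measure what the study regimen achieved. A value made negative by another regimen says nothing about that, yet these definitions look only at the result and its date. A subject whose virus returned by FU-4, who was retreated and who was negative at FU-12 would be tabulated as a success. If no later sample was taken, the subject would also count as an SVR24 success by carry-forward.

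The error runs one way: it can only raise SVR and lower the relapse count. It is also not obvious that the retreatment would be on file. Protocol 5.3 asks for medications only up to 30 days after the last dose, the last scheduled medication review is at posttreatment Week 4 (Protocol Appendix 2), and the SAP's concomitant category (7.8) ends at the last dose. At stake is the key efficacy figure of a cohort of about 20, where one subject is worth 5 percentage points.

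**Working it through.** **1. Trace the written rules.** Hypothetical subjects, all below LLOQ at end of treatment:

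| Case | HCV RNA by follow-up day | FU-12 record used | Relapse definition met? | Table category |
|---|---|---|---|---|
| A | ≥ LLOQ days 28 and 35; retreated; < LLOQ day 84 | day 84 | yes | SVR12 |
| B | ≥ LLOQ day 28 only; retreated; < LLOQ days 84 and 168 | day 84 | no | SVR12 |
| C | ≥ LLOQ days 28, 35 and 84; retreated; < LLOQ day 140 | day 140 | yes | SVR12 |
| D | ≥ LLOQ day 84 only; retreated; < LLOQ day 168 | day 84 | no | Other (SVR12 failure, SVR24 success) |

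The literal reading is therefore correct. If post-retreatment values were set aside, A and B would both become relapse: FU-12 would be missing and unbracketed, hence a failure, and the last remaining value would be positive. D stays an SVR12 failure only if no negative record falls by day 146; C shows what happens if one does.

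In A and C the subject meets a definition in SAP 6.2.1 but sits in another category in SAP 6.2.2. That is a tension between a definition and a table hierarchy, not two tables that contradict each other. The table needs some precedence so that its categories do not overlap.

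**2. Time available.** Posttreatment visits have a window of ±5 days: FU-4 on days 23 to 33, FU-12 on days 79 to 89, FU-24 on days 163 to 173.
- FU-4 to FU-12: 79 − 33 = 46 days, up to 89 − 23 = 66 days.
- FU-12 to FU-24: 163 − 89 = 74 days, up to 173 − 79 = 94 days.

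In cases A and B the positive result must come back, other therapy must be obtained and started, and the virus must fall below 15 IU/mL, all within 46 to 66 days on the visit schedule. Case C needs an unscheduled sample as well.

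**3. Size of one case.** Exact Clopper-Pearson 95% limits, the method in SAP 6.1.2. When all n succeed, the lower limit is 0.025^(1/n); for n = 20 this is 0.832. The cohort size is an assumption, since the plan says only at least 20.

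| n | Case counted as failure | Case counted as SVR12 |
|---|---|---|
| 20 | 19/20 = 95.0% (75.1 to 99.9) | 20/20 = 100% (83.2 to 100) |
| 25 | 24/25 = 96.0% (79.6 to 99.9) | 25/25 = 100% (86.3 to 100) |
| 30 | 29/30 = 96.7% (82.8 to 99.9) | 30/30 = 100% (88.4 to 100) |

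At n = 20 the tabulated relapse rate moves from 1/20 = 5.0% (0.1 to 24.9) to 0/20 (0 to 16.8). The shift of 5.0 points compares with an interval 99.9 − 75.1 = 24.8 points wide.

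**4. How many candidates.** Protocol 1.3 gives an adult SVR12 of 96% for 8 weeks in DAA-naïve subjects without cirrhosis. If adolescents respond alike, 20 × (1 − 0.96) = 0.8 subjects would miss SVR12 for any reason. Only those who relapse, are retreated and clear in time could be misclassified. The SAP confirms that "only DAA-naïve subjects without cirrhosis have been enrolled in this study". Protocol 1.1, 1.3 and 1.6 say there is no approved paediatric option after DAA failure, and Protocol 1.1 reports no relapse in two adolescent sofosbuvir-based studies. The documents give no retreatment rate, so no probability can be stated.

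**5. Would it be seen?** In A and B the FU-4 value is positive, so the subject fails SVR4, a named secondary endpoint: at n = 20, SVR4 of 95% would stand beside SVR12 of 100%. SAP 6.2.2 adds a table of subjects below and at or above LLOQ: "observed and imputed, with reasons for imputed) will be provided for each posttreatment follow-up visit". Case D shows in the SVR12/SVR24 concordance table. Protocol 8.3 provides an HCV RNA listing with reported values, Protocol 8.7.2 summaries and listings for virologic failure, and SAP 3 states "Data collected in the study will be presented in by-subject listings for all subjects in the Safety Analysis Set".

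**The case for a change.** The best case for a change is that the displays reveal an odd pattern but not its cause. Because medication recording stops 30 days after the last dose, a course started on an FU-4 result would usually fall outside required collection, and any reclassification would be decided with the data in view. There is also a quieter route. A subject negative at FU-4 who misses FU-12, is retreated elsewhere and is negative at FU-24 would have FU-12 imputed as a bracketed success, with no positive value on file. A sentence in the SAP would cost little.

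Part of this stands: the readable text has no such rule, and the bracketing route is the hardest to see, although the subject would be marked as imputed at FU-12. The rest carries less weight. A viraemic subject who turns negative with no study drug on board prompts an obvious question to the site, in a cohort small enough to read line by line. Protocol 6.6 provides unscheduled visits to confirm virologic failure, with a sequencing sample, so an unrepeated positive (cases B and D) is less likely. SAP 1 already says that changes after finalisation are documented in the study report. The SAP sentence is cheap, but it needs a therapy start date to work. Collecting that routinely would go beyond the protocol's recording period and might itself need a protocol modification, for an event that may never occur.

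**Conclusion.** The reading of the rules is right, but the plan need not change. This is a gap that analysts fill sensibly. For SVR12 it needs a rare chain of events in about 20 DAA-naïve adolescents without cirrhosis; when the relapse has been sampled it leaves a visible trace, and a single query to the site resolves it.

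The largest realistic effect is one subject: 95.0% against 100% at an assumed n = 20, or 96.7% against 100% at n = 30, with widely overlapping intervals. No decision turns on that difference. The primary endpoint is the AUCtau of each analyte, and for SVR12 the SAP says "No inferential statistics will be provided for efficacy endpoints", with no comparison and no success threshold.

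This rests on three assumptions: a cohort near the planned minimum, no more than one such case, and study staff who read the HCV RNA listing. It is limited to the readable text, since a redacted section may already contain the rule. A clarifying sentence would do no harm, but the expected result and its interpretation are the same without it.
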